11.6.2 Safety Data

Summaries and analysis of safety data will be presented for the Safety Analysis Population. All summaries and analyses will be presented for all subjects.

Solicited AEs will be summarized by severity for each day after each study vaccination (Days 1-8 post each study vaccination) and as the maximum severity over all 8 days. Additionally, solicited AEs will be analyzed by taking the most severe response over the follow-up period, dichotomizing into a binary variable (none versus mild, moderate, or severe) and using standard techniques, such as exact confidence intervals, to summarize the proportion of subjects reporting each symptom, any injection site symptom, and any systemic symptom. Summaries of solicited AEs will be presented separately for each study vaccination as well as overall study vaccinations by treatment arm. The proportion of subjects reporting symptoms may be compared between

treatment arms using Chi-square or Fisher's exact test. The proportion of subjects reporting solicited symptoms between the different study vaccinations (i.e., first vs. second, first vs. third, second vs. third, as applicable within each study group) will be compared using McNemar's test.

Unsolicited AEs will be coded by Medical Dictionary for Regulatory Activities (MedDRA®) for preferred term and system organ class (SOC). The numbers of SAEs and MAAEs, including NOCMCs and PIMMCs, are likely to be small in this trial and will be reported by detailed listings showing the event description, MedDRA® preferred term and SOC, relevant dates (study vaccinations and AEs), severity, relatedness, and outcome for each event. Non-serious unsolicited AEs will be summarized as number and percentage of subjects reporting at least one event in each MedDRA® preferred term and SOC, cross tabulated by severity and relationship to study product. Additionally, the proportion of subjects and exact 95% CIs of AEs in aggregate and by MedDRA® categories will be computed.

Clinical laboratory data will be summarized by severity for each visit and as the maximum over all post-study vaccination visits. Graphical presentations may include box plots.

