For each systemic and local event, any systemic event, any local event, and any solicited event, the maximum severity over 7 days after each vaccination will be summarized for the Safety population. The number and percentage of subjects reporting each event will be summarized by the maximum severity and treatment group, separately for each dose and over all doses. For each event the denominator is the number of subjects who received the applicable vaccination with non-missing data for the specific event. The 95% CI calculated using Clopper-Pearson methodology from a binomial distribution (SAS Proc Freq with a binomial option) will be presented ([Table 108](#), [Table 109](#), [Table 110](#), [Table 111](#)).

The number of subjects reporting a solicited adverse event will be summarized for each day post vaccination for each vaccination and for all vaccinations combined both in a summary table ([Table 112](#), [Table 113](#), [Table 114](#), [Table 115](#)) and graphically in a bar chart ([Figure 52](#) and [Figure 53](#)). A comparison of the event rate for each treatment group between study vaccinations will be presented for those groups receiving multiple vaccinations, including p-values from McNemar's test performed ([Table 116](#), [Table 117](#)).

Systemic and Local solicited events reported by subject will be presented in [Listing 10](#) and [Listing 11](#), sorted by subject ID, vaccination number, parameter, and study day.

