9.3.2. Unsolicited Adverse Events

When calculating the incidence of unsolicited AEs (i.e., on a per subject basis), each subject will only be counted once at the highest severity and/or relationship, and any repetitions of AEs within a subject will be ignored; the denominator will be the total number of subjects in the safety population. All AEs reported will be included in the summaries and analyses.

The number and percentage of subjects reporting at least one unsolicited AE will be summarized by MedDRA system organ class and preferred term. A 95% CI will be presented for the percentage of subjects reporting any unsolicited AE (serious or non-serious) for each MedDRA system organ class and preferred term over all study vaccinations ([Table 118](#)).

The following summaries for unsolicited AEs will be presented by MedDRA system organ class, preferred term, and treatment group:

- Incidence of AEs by severity and relationship to study product ([Table 119](#));
- Incidence of non-serious, related AEs by severity ([Table 120](#));
- Incidence of AEs over time (Days 1-8, Days 9-22 post each study vaccination) ([Table 121](#));

- Incidence of non-serious, related AEs over time (Days 1-8, Days 9-22 post each study vaccination) ([Table 122](#)) – note this table presents results for secondary safety endpoint, “Occurrence of study vaccine-related unsolicited non-serious AEs from the time of each study vaccination through approximately 21 days after each study vaccination”;
- Total frequency of AEs over time (Days 1-8, Days 9-22 post each study vaccination) ([Table 123](#));
- Subject listing of non-serious AEs of moderate or greater severity ([Table 128](#));
- Bar chart displaying total frequency of AEs by severity and MedDRA system organ class and treatment group ([Figure 54](#));
- Bar chart displaying incidence of AEs by severity and MedDRA system organ class, and treatment group ([Figure 55](#));
- Bar chart displaying total frequency and incidence of AEs by relationship to study product, MedDRA system organ class, and treatment group ([Figure 56](#) and [Figure 57](#)).

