12. SUMMARY OF CHANGES IN THE CONDUCT OF THE STUDY OR PLANNED ANALYSES

This SAP does not include any changes from the analyses described in the protocol.

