9.1 Overall Study Design and Plan Description

Table 1: Study Design

	Day 1 Dose 1	Approximately Day 22 Dose 2	Approximately Day 43 Dose 3
Group 1 (Age 19-64) n=60	Dose 1 (First and Second Study Vaccinations): Sanofi Pasteur H7N9 vaccine 3.75 mcg/ PBS diluent, plus GSK AS03 adjuvant + IIV4	Dose 2 (Third Study Vaccination): Sanofi Pasteur H7N9 vaccine 3.75 mcg/ PBS diluent, plus GSK AS03 adjuvant	N/A
Group 2 (Age 19-64) n=60	Dose 1 (First Study Vaccination): IIV4	Dose 2 (Second Study Vaccination): Sanofi Pasteur H7N9 vaccine 3.75 mcg/ PBS diluent, plus GSK AS03 adjuvant	Dose 3 (Third Study Vaccination): Sanofi Pasteur H7N9 vaccine 3.75 mcg/ PBS diluent, plus GSK AS03 adjuvant
Group 3 (Age 19-64) n=30	Dose 1 (First Study Vaccination): IIV4	N/A	N/A
Total Enrollment, n = ~150	
Blood for HAI/Neut assays for 2017 H7N9 IIV will be collected:
 
 for Group 1 on Days 1 (baseline), 22, and 43, and at approximately 180 days post second adjuvanted 2017 H7N9 IIV dose (Day 202) for Group 2, on Days 22 (baseline), 43, and 64, and at approximately 180 days post second 2017 H7N9 IIV dose (Day 223). 
Serological antibody assays will also be performed against the vaccine viruses in IIV4 from serum samples collected at baseline (Day 1) and approximately 21 and 180 days following receipt of IIV4 (Groups 1, 2 and 3).
 
Safety Lab Timepoints:
 
Group 1: 4 timepoints per subject (Days 1, 8, 22, and 29) Group 2: 6 timepoints per subject (Days 1, 8, 22, 29, 43, and 50) Group 3: 2 timepoints per subject (Days 1 and 8) and Early Termination and /or Unscheduled Visits
		

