Study Dose 2 vs Study Dose 3				
Group 2: Sequential Administration (N=X)	Subjects with No Symptoms	x (%)	x (%)	x (%)
	Subjects with Mild or Greater Symptoms	x (%)	x (%)	x (%)
	Total Number of Subjects	x (%)	x (%)	x (100%) [0.xxx]

Note: Denominators for percentages are the number of subjects in the safety population who received both the first and second study dose. Subjects who did not receive both indicated doses are not included in this table. [x] subjects did not receive the second dose and [x] subjects did not receive the third dose.
* P-value is calculated from McNemar's test for each treatment group.

Table with similar format:

Table 117: Comparison of the Number and Percentage of Subjects Experiencing Solicited Local Events by Dose and Treatment Group – Safety Population

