16.2.7 Adverse Events

Listing 10: 16.2.7.1 - Solicited Events – Systemic Symptoms

Subject ID	Treatment Group	Dose Number	Post Dose Day	Assessment ¹	Symptom	Severity	Attributed to Alternate Etiology? ²	Alternate Etiology
				MA				
				Clinic				

¹ MA = Data reported by subject on the Memory Aid and reviewed by clinic staff and reported in Solicited Events eCRF.
 Clinic = Data collected by clinic staff during physical exam or symptom assessment (treatment administration record, in-clinic assessment, etc.)
² Grade 3 events only.

Listing 11: 16.2.7.2 - Solicited Events – Local Symptoms

[Implementation Note: For group 1, dose 1 match the product received to symptoms reported based on the arm the product (IIV4, A/H7N) was received in]

Subject ID	Treatment Group	Dose Number	Product Received ¹	Post Dose Day	Assessment ²	Symptom	Severity
					MA		
					Clinic		

¹ For Group 1, IIV4 and A/H7N9 vaccines are both received at Dose 1 in separate arms.

² MA = Data reported by subject on the Memory Aid and reviewed by clinic staff and reported in Solicited Events eCRF.

Clinic = Data collected by clinic staff during physical exam or symptom assessment (treatment administration record, in-clinic assessment, etc.)

Listing 12: 16.2.7.3 - Unsolicited Adverse Events

Adverse Event	Associated with Dose #	# of Days Post Associated Dose (Duration)	Severity	SAE? MAAE? PIMMC?	Relationship to Study Treatment	In Not Related, Alternative Etiology	Action Taken with Study Treatment	Subject Discontinued Due to AE	Outcome	MedDRA® System Organ Class	MedDRA® Preferred Term
Subject ID: , Treatment Group: , AE Number:											
				SAE: No MAAE: Yes PIMMC: No							
Comments:											
Subject ID: , Treatment Group: , AE Number:											
Comments:											
Note: For additional details about SAEs, see Section 14.3.3											

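### The safety shells work by dose, not by study vaccination: Group 1's local McNemar test sets two injection sites against one, and later-dose unsolicited AE percentages include subjects never given the dose

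*SAP*

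**What the plan says.** **Protocol.** Section 11.6.2 states: "Summaries of solicited AEs will be presented separately for each study vaccination as well as overall study vaccinations by treatment arm". It adds that the proportions reporting solicited symptoms will be compared by McNemar's test between study vaccinations: "first vs. second, first vs. third, second vs. third, as applicable within each study group".

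**Units.** The study design table (Table 1 in both documents) keeps dose and study vaccination apart. Group 1's Day 1 entry begins "Dose 1 (First and Second Study Vaccinations", and its Day 22 injection is Dose 2, the third study vaccination. Protocol 6.2 puts the two Day 1 injections in opposite arms.

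**SAP, solicited events.** Section 9.3.1 moves between the two terms. Its maximum-severity summary is by dose: results "will be summarized by the maximum severity and treatment group, separately for each dose and over all doses". All the solicited tables (102 to 105 and 108 to 117) are by study dose, with no row for arm or product. Each subject counts once, at highest severity. Table 117 is titled "Comparison of the Number and Percentage of Subjects Experiencing Solicited Local Events by Dose and Treatment Group" and takes the layout of Table 116, so Group 1 has one contrast, Dose 1 against Dose 2. Product is tied to arm only in Listing 11, whose note reads "For group 1, dose 1 match the product received to symptoms reported based on the arm".

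**SAP, unsolicited events.** Section 9.3.2 says "the denominator will be the total number of subjects in the safety population". The footnotes of Tables 121 and 122 repeat this for every column.

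**SAP 12.** "This SAP does not include any changes from the analyses described in the protocol".

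**The concern.** Combining one dose column with the count-once rule gives an either-arm rate for Group 1 on Day 1. That rate is a valid measure of what a subject experiences after simultaneous vaccination. It does not show how the H7N9 site or the IIV4 site behaves when both vaccines are given together, and no summary table does. Tables 103, 109 and 113 and Figure 53 are affected.

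In Table 117 the Group 1 test compares an either-of-two-sites rate at Dose 1 with a one-site rate at Dose 2. A higher Dose 1 rate can come from the extra injection alone, so the p-value cannot be read as a change in H7N9 local reactogenicity from first to second dose. Two of the three Group 1 local contrasts implied by Protocol 11.6.2 are missing, and SAP 12 declares no change.

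Tables 121 and 122 raise a separate denominator problem. Someone who never received Dose 2 has no post-Dose 2 period and cannot enter that numerator, yet stays in the denominator. Protocol 8.2.4, 8.3.4 and 8.3.7 also limit AE collection in such subjects to SAEs and MAAEs. SAP 9.3.2 names Table 122 as the display for a secondary safety endpoint.

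**Working it through.** **Plan figures.** Neither document states a reaction rate, so there is no figure on this point to reproduce. The nearest, SAP Table 8, is correct and not in dispute: 1 − 0.99^60 = 45.3% (stated 45).

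**1. Contrasts for Group 1, local events**

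| Pair of study vaccinations | Injections | In Table 117? |
|---|---|---|
| First and second | Day 1 H7N9 arm and Day 1 IIV4 arm | No |
| Each Day 1 vaccination v third | Day 1 H7N9 arm v Day 22 H7N9; Day 1 IIV4 arm v Day 22 H7N9 | Merged into one test: either arm v Day 22 |

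Three contrasts become one, and that one does not match sites.

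**2. Gap created by the extra site.** Let a be the IIV4-arm local rate on Day 1 and b the H7N9-arm local rate, equal at both H7N9 doses (no true dose effect). Then

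Dose 1 rate − Dose 2 rate = P(IIV4 arm or H7N9 arm reacts) − b = P(IIV4 arm reacts and H7N9 arm does not).

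This lies between max(0, a − b) and min(a, 1 − b), and equals a(1 − b) under independence.

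- a = 0.1, b = 0.2: range 0 to 10 points; independence 0.1 × 0.8 = 8 points.
- a = 0.4, b = 0.6: range 0 to 40 points; independence 0.4 × 0.4 = 16 points.

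**3. Effect on the McNemar test.** Pairs: 60 × 0.85 = 51, using the up-to-15% loss in Protocol 11.4.2. Within-subject dependence is an equal latent normal correlation among the three injection sites. Cell probabilities come from 2,000,000 draws, and rejection at two-sided 0.05 is enumerated over discordant counts. The SAP does not say which form of the test is meant, so entries are exact (uncorrected asymptotic).

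| Correlation | Gap, a=0.1, b=0.2 | Rejection | Gap, a=0.4, b=0.6 | Rejection |
|---|---|---|---|---|
| 0 | 8 points | 10.6% (15.6%) | 16 points | 32.1% (41.7%) |
| 0.3 | 6 | 8.3% (12.4%) | 11 | 20.4% (27.8%) |
| 0.6 | 4 | 5.0% (8.4%) | 7 | 9.5% (14.0%) |
| 0.8 | 2 | 2.5% (6.1%) | 3 | 3.8% (6.8%) |

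Comparing H7N9 arm with H7N9 arm under the same settings rejects in 1.7 to 3.0% (exact) or 4.3 to 5.4% (uncorrected).

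A wider set of assumed rates (H7N9 30 to 70%, IIV4 30 to 50%, correlation 0 to 0.6, 60 pairs, uncorrected test) gives gaps of about 6 to 25 points and rejection of about 15 to 82%, against about 5% like for like.

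**4. Denominator.** With x subjects reporting an event, N in the Safety population and r recipients of the dose, the SAP percentage divided by the recipient percentage is (x/N)/(x/r) = r/N. The relative understatement is therefore the fraction who missed the dose. For N = 60 and x = 6:

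| Missed dose | SAP percentage | Percentage of recipients |
|---|---|---|
| 0 | 6/60 = 10.0% | 10.0% |
| 3 (5%) | 10.0% | 6/57 = 10.5% |
| 6 (10%) | 10.0% | 6/54 = 11.1% |
| 9 (15%) | 10.0% | 6/51 = 11.8% |

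**The case against.** **The protocol wording allows latitude.** Contrasts are required only as applicable within each group, and parts of SAP 9.3.1 do speak of each vaccination. The latitude fits systemic events, which cannot be assigned to one of two injections given within 15 minutes. It does not fit local events, which are recorded by arm. The SAP text being partly right does not help when the shells produce something else.

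**The either-arm rate answers the schedule question.** That is true, and it should stay. Per-product rows are additional to it.

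**Group 2 already has a clean test.** Its Dose 2 v Dose 3 row compares first with second H7N9 dose, one site each. This stands and reduces the harm, but it carries no information about co-administration and leaves the Group 1 row confounded.

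**The displays are descriptive.** The trial tests no formal hypothesis, and Tables 117, 121 and 122 are outside the preliminary report. This limits the consequence. However, Tables 103 and 109 are marked for that report, which the SAP treats as the final analysis of those data.

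**The size rests on assumed rates.** That is correct. At the lower pair of rates the exact test is at or below its nominal level from correlation 0.6 upward, and two arms of one person are plausibly correlated.

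**The denominator effect is small and openly stated.** It is small, and Table 19 would let a reader recompute group totals. The rule still contradicts the SAP's own solicited rule, which counts recipients only.

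**Conclusion.** The concern holds. That the shells depart from Protocol 11.6.2 for Group 1 local events, without being declared in SAP 12, follows from the documents alone and needs no assumed rate. So does the mismatch of two sites against one in Table 117.

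The size depends on unknown reaction rates and within-subject dependence. It is material under weak dependence (up to 32% exact rejection in the two main scenarios, against about 3% on the H7N9 arm alone) and disappears under strong dependence.

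The denominator error always runs towards understatement. It is 0 if nobody misses a dose and at most 15% relative; the real figure is probably smaller, because the 15% also covers loss to follow-up and other protocol deviations.

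Unaffected are systemic rows, the Dose 2 and Dose 3 solicited tables, solicited results for Groups 2 and 3, Tables 118 to 120, the event counts in Table 123, and the Dose 1 and any-dose columns of Tables 121 and 122. This should be corrected before the analysis. It does not threaten the primary immunogenicity results.

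**What to change.** 1. In Tables 103, 109 and 113 and Figure 53, add H7N9-arm and IIV4-arm rows or panels for Group 1 Dose 1 local events, using the arm-matched data behind Listing 11. Keep the either-arm row.
2. In Table 117, base Group 1 Dose 1 v Dose 2 on the H7N9 arm.
3. Either add the other two Group 1 local contrasts (H7N9 arm v IIV4 arm on Day 1; Day 1 IIV4 arm v Day 22 injection) or record their omission in SAP 12.
4. Use dose and vaccination consistently in SAP 9.3.1, in the sense of Table 1.
5. In SAP 9.3.2 and Tables 121 and 122, divide each post-dose column by the number in the group who received that dose. The any-dose column stays as it is.

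The cost is a few rows or panels, one redefined comparison and one denominator. Arm-level symptoms are already collected, and Table 19 already counts the recipients of each dose.

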9.3.2. Unsolicited Adverse Events

When calculating the incidence of unsolicited AEs (i.e., on a per subject basis), each subject will only be counted once at the highest severity and/or relationship, and any repetitions of AEs within a subject will be ignored; the denominator will be the total number of subjects in the safety population. All AEs reported will be included in the summaries and analyses.

The number and percentage of subjects reporting at least one unsolicited AE will be summarized by MedDRA system organ class and preferred term. A 95% CI will be presented for the percentage of subjects reporting any unsolicited AE (serious or non-serious) for each MedDRA system organ class and preferred term over all study vaccinations ([Table 118](#)).

The following summaries for unsolicited AEs will be presented by MedDRA system organ class, preferred term, and treatment group:

- Incidence of AEs by severity and relationship to study product ([Table 119](#));
- Incidence of non-serious, related AEs by severity ([Table 120](#));
- Incidence of AEs over time (Days 1-8, Days 9-22 post each study vaccination) ([Table 121](#));

- Incidence of non-serious, related AEs over time (Days 1-8, Days 9-22 post each study vaccination) ([Table 122](#)) – note this table presents results for secondary safety endpoint, “Occurrence of study vaccine-related unsolicited non-serious AEs from the time of each study vaccination through approximately 21 days after each study vaccination”;
- Total frequency of AEs over time (Days 1-8, Days 9-22 post each study vaccination) ([Table 123](#));
- Subject listing of non-serious AEs of moderate or greater severity ([Table 128](#));
- Bar chart displaying total frequency of AEs by severity and MedDRA system organ class and treatment group ([Figure 54](#));
- Bar chart displaying incidence of AEs by severity and MedDRA system organ class, and treatment group ([Figure 55](#));
- Bar chart displaying total frequency and incidence of AEs by relationship to study product, MedDRA system organ class, and treatment group ([Figure 56](#) and [Figure 57](#)).

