New-Onset Chronic Medical Conditions (NOCMCs): NOCMCs are defined as any new ICD-10 diagnosis that is applied to the subject during the duration of the study, after receipt of the study agent, that is expected to continue for at least 3 months and requires continued health care intervention.

Medically-Attended Adverse Events (MAAEs): For each unsolicited AE experienced, the subject will be asked if he/she had received medical attention, defined as hospitalization, an ER visit, or an otherwise unscheduled visit to or from medical personnel for any reason. AEs characterized by such unscheduled medical care will be designated as MAAEs.

Potentially Immune-Mediated Medical Conditions (PIMMCs): PIMMCs constitute a group of AEs that includes diseases which are clearly autoimmune in etiology and other inflammatory and/or neurologic disorders which may or may not have autoimmune etiologies. PIMMCs currently in effect are presented in [Appendix B: List of PIMMCs](#).

Severity of Event: AEs will be assessed by a licensed study clinician listed on the Form FDA 1572 as the site principal investigator or appropriate sub-investigator using a protocol-defined grading system (see [Sections 9.2.2](#) and [9.2.3](#)). For events not included in the protocol-defined grading system, the following guidelines will be used to quantify severity:

- **Mild (Grade 1)**: Events require minimal or no treatment and do not interfere with the subject's daily activities.
- **Moderate (Grade 2)**: Events result in a low level of inconvenience or concern with therapeutic measures. Moderate events may cause some interference with functioning and daily activities.
- **Severe (Grade 3)**: Events interrupt the subject's daily activities and may require systemic drug therapy or other treatment. Severe events are usually incapacitating.

Relationship to Study Product: The licensed study clinician's assessment of an AE's relationship to study product is part of the documentation process, but it is not a factor in determining what is or is not reported in this trial. If there is any doubt as to whether a clinical observation is an AE, the event should be reported. The relationship to study product must be assessed for AEs using the terms: related or not related. In a clinical trial, the study product must always be suspect. To help assess, the following guidelines are used:

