3.2.2. Secondary

Safety:

- Occurrence of study vaccine-related unsolicited non-serious AEs following each study vaccination through approximately 21 days after each study vaccination.
- Occurrence of all unsolicited non-SAEs following each study vaccination through approximately 21 days after each study vaccination.
- Occurrence of MAAEs, including NOCMCs and PIMMCs, following the first study vaccination through approximately 12 months after the last study vaccination.

Immunogenicity:

- For HAI and Neut antibodies, percentage of subjects achieving seroconversion against the 2017 H7N9 vaccine strain at approximately 21 days after receipt of 1 dose of AS03-adjuvanted 2017 H7N9 IIV (Group 1– Day 22; Group 2 – Day 43; Group 3 – N/A).
- For HAI and Neut antibodies, percentage of subjects achieving serum HAI and Neut antibody titers $\geq 1:40$ against the influenza 2017 H7N9 vaccine strain at baseline and approximately 21 days after receipt of 1 dose of AS03-adjuvanted 2017 H7N9 IIV (Group 1–Day 1 (baseline) and Day 22; Group 2 –Day 22 (baseline) and Day 43; Group 3 – N/A).
- GMTs of serum HAI and Neut antibodies against the influenza 2017 H7N9 vaccine virus at baseline and at approximately 21 days after receipt of 1 dose of AS03-adjuvanted 2017 H7N9 IIV. (Group 1–Day 1 (baseline) and Day 22; Group 2 –Day 22 (baseline) and Day 43; Group 3 – N/A).

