4.5.1. Safety Variables

Safety will be assessed by the frequency and severity of:

1. SAEs occurring from the time of the first study vaccination through approximately 12 months after the last study vaccination.
2. Solicited AEs – reactogenicity events occurring from the time of each study vaccination through 7 days after each study vaccination:
 - a) Injection site reactions including pruritus, ecchymosis, erythema, induration (hardness)/edema (swelling), pain, and tenderness.
 - b) Systemic reactions including fever, feverishness, fatigue, malaise, myalgia, arthralgia, headache, and nausea.
3. Clinical safety laboratory AEs occurring from the time of each study vaccination through approximately 7 days after each study vaccination. Parameters to be evaluated include white blood cells (WBC), hemoglobin (Hgb), platelets (PLT), alanine aminotransferase (ALT), total bilirubin (T. Bili), and creatinine (Cr).
4. Unsolicited AEs – non-serious AEs occurring from the time of each study vaccination through approximately 21 days after each study vaccination.
5. MAAEs, including NOCMCs, and PIMMCs occurring from the time of the first study vaccination through approximately 12 months after the last study vaccination.

Grading scales for injection site and systemic solicited reactions, vital signs, and clinical laboratory parameters are provided in [Table 13](#), [Table 14](#), [Table 15](#), and [Table 16](#).

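### No SAP table reports the secondary endpoint of all non-serious unsolicited AEs within 21 days: Table 121 comes close, and Tables 118 and 119 have no onset window and include serious events

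*SAP*

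**What the plan says.** SAP 3.2.2 has two secondary endpoints for unsolicited AEs. One covers vaccine-related non-serious events. The other covers non-serious events of any cause: "Occurrence of all unsolicited non-SAEs following each study vaccination through approximately 21 days after each study vaccination". SAP 4.5.1 uses the same scope when it defines unsolicited AEs as "non-serious AEs occurring from the time of each study vaccination through approximately 21 days after each study vaccination". It lists medically attended events as a separate variable with a longer window: "MAAEs, including NOCMCs, and PIMMCs occurring from the time of the first study vaccination through approximately 12 months after the last study vaccination".

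SAP 9.3.2 sets the scope of the tables differently: "All AEs reported will be included in the summaries and analyses". Table 118 is to give a 95% CI for the percentage of subjects reporting "any unsolicited AE (serious or non-serious) for each MedDRA system organ class and preferred term over all study vaccinations". A note in that section names Table 122 as the display for the vaccine-related endpoint. No table is named for the all-causality endpoint.

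Protocol 11.6.2 sends SAEs and MAAEs to detailed listings and says "Non-serious unsolicited AEs will be summarized as number and percentage of subjects reporting at least one event", by preferred term and SOC, cross-tabulated by severity and relationship. Its next sentence adds exact CIs for AEs in aggregate and by MedDRA category. SAP 12 states that nothing has changed from the protocol's analyses.

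**The concern.** A prespecified secondary endpoint should have one identifiable display that counts the events in its definition. Here a reader looking for the all-causality result would probably turn to Table 118, because it has the CIs, or to Table 119, because it is the severity-by-relationship table that the protocol describes. Both are marked for the Preliminary Report, which may support publication and counts as the final analysis of its data. Neither has the endpoint's scope.

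The missing window matters because collection changes after 21 days. Inside the window every unsolicited AE is collected. Outside it, only SAEs and MAAEs (including NOCMCs and PIMMCs) are. A count with no window mixes the two, and at Day 64 the share of each differs by group.

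**Working it through.** The check compares each display with the endpoint definition and then takes day counts from the visit schedule. The plan gives no figure to reproduce.

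**Step 1. Displays against the endpoint.** Sources are SAP 9.3 and 9.3.2, the table shells, and the asterisks that mark the Preliminary Report.

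| Display | Non-serious only | All causality | 21-day window | CI | Preliminary Report |
|---|---|---|---|---|---|
| Table 100 (unsolicited row) | no | yes | no | no | yes |
| Table 101 (non-serious block, events in at least 5% of subjects) | yes | yes | no | no | no |
| Table 118 | no | yes | no | yes | yes |
| Table 119 | no | yes | no | no | yes |
| Table 120 | yes | no, related only | no | no | no |
| Table 121 | no | yes | yes | no | no |
| Table 122 | yes | no, related only | yes | no | no |
| Table 123 (event counts) | no | yes | yes | no | no |
| Table 128 (listing, moderate or severe) | yes | yes | no | no | yes |
| Figures 54-57 | no | yes | no | no | no |

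No display has yes in all of the first three columns. Table 121 fails on one of them. Its Dose 3 columns also need correcting: all three are headed Day 1-8, where Table 123 has Days 1-8, 9-22 and 1-22.

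**Step 2. Table 119 against the protocol.** Protocol 11.6.2 plans the severity-by-relationship summary for non-serious unsolicited AEs. Table 119 is that summary without the restriction, and SAP 12 does not record the difference.

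**Step 3. Do later medically attended events enter Tables 118 and 119?** Three facts point to yes:
- Protocol 9.2.1 builds the MAAE category out of unsolicited AEs: "For each unsolicited AE experienced, the subject will be asked if he/she had received medical attention".
- The shell of Listing 12, the unsolicited-AE listing, has SAE, MAAE and PIMMC flags (its example row reads "SAE: No MAAE: Yes PIMMC: No").
- Neither table states an onset window, and the rule is to include every reported AE.

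No sentence says so directly, so this is an inference.

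**Step 4. Length of SAE/MAAE-only follow-up, by nominal schedule.** Full collection ends 21 days after the last dose: Day 43 in Group 1, Day 64 in Group 2 and Day 22 in Group 3. The final contacts are on Days 387, 408 and 366.

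| Group | Full collection (days) | SAE/MAAE-only days to Day 64 | SAE/MAAE-only days to final contact |
|---|---|---|---|
| 1 | 43 − 1 = 42 | 64 − 43 = 21 | 387 − 43 = 344 |
| 2 | 64 − 1 = 63 | 64 − 64 = 0 | 408 − 64 = 344 |
| 3 | 22 − 1 = 21 | 64 − 22 = 42 | 366 − 22 = 344 |

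The groups differ at Day 64 and are equal at the end of follow-up.

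**The case against.** The strongest reply is that Table 121 is already the endpoint table. It is all-causality, windowed, and shown by dose and after any dose. If unsolicited AEs are non-serious by the SAP 4.5.1 definition, nothing is missing but a label. Protocol 11.6.2 expects few SAEs, and Table 124 lists them, so any inside the window can be found. Much of this stands: Table 121 should come close to the endpoint numerically. But the 4.5.1 reading conflicts with the wording for Table 118 and would make the non-serious qualifier on Tables 120 and 122 redundant. Table 121 is also outside the Preliminary Report and is not identified with the endpoint as Table 122 is with its own.

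Second, the protocol itself asks for Table 118 through its sentence on exact CIs for AEs in aggregate. That stands. A reader might infer that Table 118 breaks the protocol and must be narrowed; it does not, and it can remain as the all-AE table. What it lacks is a stated window.

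Third, the entry of 12-month MAAEs is not stated. SAP 4.5.1 and Table 100 treat MAAEs separately from unsolicited AEs, SAP 9.4 gives them their own listing, and the Listing 12 flag fits MAAEs inside the window equally well. That also stands, which is why Step 3 is offered only as the likelier reading.

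Fourth, a CI is not part of the endpoint's definition, and the study is descriptive. That is fair. The CI is recommended because Protocol 11.6.2 plans exact CIs for AE proportions.

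**Conclusion.** The point holds as a gap in the reporting plan. One secondary endpoint has no table with its scope, and Table 119 departs from the protocol without a declared change. Both follow directly from the text.

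The mixing of complete and SAE/MAAE-only collection in Tables 118 and 119 rests on the inference in Step 3 and on nominal visit days. If it is right, Preliminary Report percentages would cover 42, 21 and 0 extra days in Groups 3, 1 and 2, so they would not be like for like across groups.

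The documents do not support three stronger readings:
- That the IIV4-only group is worst affected over the whole study. The added time is 344 days in every group. Group 3 differs only in share, with 21 of 365 days fully collected (6%).
- That the printed rate would roughly double. For example, 20% within the window and 25% later, taken as independent, gives 1 − 0.80 × 0.75 = 40%. Neither rate is in the documents, and the size of the effect cannot be derived from them.
- That Table 118 will certainly change between the Preliminary Report and the CSR. SAP 6.2.1 treats the preliminary analyses as final for their data. Whether the CSR version adds later events depends on the window that the SAP leaves unstated.

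**What to change.** - Restrict Table 121 to non-serious unsolicited AEs with onset on Days 1-22 after each dose and after any dose. Add exact 95% CIs, label it as the all-causality secondary endpoint, mark it for the Preliminary Report and correct its Dose 3 column heads.
- Restrict Table 119 to non-serious AEs, as in Protocol 11.6.2, or declare the change in SAP 12.
- Keep Table 118 as the all-AE aggregate, but state its onset window.
- Reconcile the definition in SAP 4.5.1 with the inclusion rule in SAP 9.3.2.
- Leave SAEs, MAAEs, NOCMCs and PIMMCs in Tables 100 and 124-127.

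The cost is SAP wording and a filter on onset day and seriousness. No new data are needed.
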